13.2 Secondary Efficacy Analyses

Secondary analyses of the primary efficacy endpoint include repeating the primary analysis strategy using observed data only, and LOCF where LOCF will be performed using time-relevant measures. These analyses will also be repeated on the PP population to determine robustness of results.

Additionally, secondary analyses of the primary endpoint will be completed using the two-sample t-test and 95% t-distribution CIs on the difference (netarsudil (0.01%, 0.02%, and 0.04%) - placebo) for each comparison.

The secondary efficacy endpoints include:

- Mean of Mean diurnal IOP at Weeks 1 and 2 (Days 8 and 15, respectively)
- Mean change from baseline in mean diurnal IOP at each post-treatment visit
- Mean percent change from baseline in mean diurnal IOP at each post-treatment visit

- Mean IOP at each post-treatment time point
- Mean change from diurnally-adjusted baseline IOP at each post-treatment time point
- Mean percent change from diurnally-adjusted baseline IOP at each post-treatment time point
- Percentages of subjects achieving pre-specified mean, mean change, and percent mean change in mean diurnal IOP levels

Similar ANCOVA models for primary efficacy endpoint will be used for mean of mean diurnal IOP at Weeks 1 and 2, and mean IOP at each post-treatment time point (09:00, 11:00, and 16:00 at the Week 1, Week 2, and Week 4 Visits).

Additionally, for IOP at each post-treatment time point, mixed model repeated measures (MMRM) will be run with baseline time-matched IOP as a covariate; treatment, visit, time point, treatment by visit, treatment by time point, visit by time point, and treatment by visit by time point as fixed effects; and subject as a repeated measure, using an unstructured covariance matrix. The LS mean differences (netarsudil – placebo) will be presented separately for netarsudil 0.01%, 0.02%, and 0.04% as well as two-sided p-values and 95% CIs. This analysis will be performed for the ITT population with observed data only.

Two-sample t-test and 95% t-distribution confidence intervals on the difference (netarsudil [0.01%, 0.02%, and 0.04%] - placebo) will be used for mean change from baseline in mean diurnal IOP at each post-treatment visit, mean change from diurnally-adjusted baseline IOP at each post-treatment time point, mean percent change from baseline in mean diurnal IOP at each post-treatment visit, and mean percent change from diurnally-adjusted baseline IOP at each post-treatment time point.

The number and percentage of study eyes obtaining a mean diurnal IOP of ≤ 22 to ≤ 14 mmHg in 1 mmHg increments will be summarized at Week 1, Week 2, and Week 4. Analyses of IOP will also be summarized by the number and percentage of study eyes achieving mean diurnal IOP reduction from baseline of ≥ 4 to ≥ 12 mmHg in 2 mmHg increments and percent reduction from baseline of $\geq 5\%$ to $\geq 40\%$ in 5% increments at Week 1, Week 2, and Week 4. Fisher's exact test (two-sided p-values) will be used to test differences between netarsudil (0.01, 0.02%, or 0.04%) versus placebo for each category at each visit. These analyses will be presented for both the ITT and PP populations with observed data only.

All primary and secondary efficacy variables, along with the corresponding planned analysis methods, are presented in Table 13-1.

Table 13-1. Summary of Efficacy Variables and Analysis Methods

	Two Sample t-test ^a	ANCOVA ^b	MMRM ^c	Fisher's Exact Test ^d	Analysis Population	Missing Data Imputation
Primary Analysis						
Mean of Mean diurnal IOP at Week 4		X			ITT	MCMC
Secondary Analyses						
Mean of Mean diurnal IOP at Week 4	X	X			ITT	MCMC, LOCF, Observed Data
Mean of Mean diurnal IOP at Week 1 and Week 2	X	X			ITT	MCMC, LOCF, Observed Data
Mean diurnal IOP at Week 1, Week 2 and Week 4	X	X			PP	MCMC, LOCF, Observed Data
Mean change from baseline in mean diurnal IOP at each post-treatment visit	X				ITT, PP	MCMC, LOCF, Observed Data
Mean percent change from baseline in mean diurnal IOP at each post-treatment visit	X				ITT	Observed Data
Mean IOP at each post-treatment time point	X	X			ITT, PP	MCMC, LOCF, Observed Data
Mean IOP at each post-treatment visit			X		ITT	Observed Data
Mean change from diurnally adjusted baseline IOP at each post-treatment time point	X				ITT, PP	MCMC, LOCF, Observed Data
Mean percent change from diurnally adjusted baseline IOP at each post-treatment time point	X				ITT	Observed data
Percentages of subjects achieving pre-specified mean, mean change, and percent mean change diurnal IOP levels				X	ITT, PP	Observed data

^a Two sample t-test comparing actual mean diurnal IOP or mean IOP value at each time point between each netarsudil group and placebo.

^b ANCOVA model including treatment as the main effect and baseline as the covariate. Individual models will be fit for each visit and time point.

^c Mixed model repeated measures analysis has treatment, visit, time point, treatment*visit, treatment*time point, visit*time point, and treatment*visit*time point as fixed effects, time-matched baseline IOP as covariate, visit*time point within a subject as repeated measures, using an unstructured covariance matrix.

^d Fisher's exact test comparing the incidence in each category at each time point between each netarsudil group and placebo.

Additionally, mean IOP with standard error (SE) will be displayed graphically. A Subject Listing of IOP will also be produced.

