Mean percent change from baseline in mean diurnal IOP and mean percent change from diurnally adjusted baseline IOP at each time point will be analyzed using two-sample t-tests, between netarsudil (0.01%, 0.02% or 0.04%) and placebo, at each time point and visit, including two-sample t-tests and 95% t-distribution confidence intervals on the difference (netarsudil - placebo).

Mean diurnal IOP values will be constructed by averaging the 3 diurnal IOP measurements on each of Week 1, Week 2, and Week 4 visits. Mean diurnal baseline IOP will be constructed as the average of the three Day 1 IOP measurements. Mean change from mean baseline diurnal IOP will be created by taking the average of the 3 time points on each of Week 1, Week 2, and Week 4 visits and subtracting the single mean baseline diurnal IOP measurement.

Sub-group analyses based upon pre-study characteristics such as site, demographics, baseline IOP categories, or pre-study ocular hypotensive medications may be completed to further investigate the efficacy measures.

Analyses of IOP will also include summarizing the number and percentage of study eyes achieving mean diurnal IOP reduction from baseline of ≥ 4 to ≥ 12 mmHg in 2 mmHg increments and percent reduction from baseline of $\geq 5\%$ to $\geq 40\%$ in 5% increments at Week 1, Week 2, and Week 4. Additionally, the number and percentage of study eyes attaining a mean diurnal IOP of ≤ 22 to ≤ 14 mmHg in 1 mmHg increments will be summarized at Week 1, Week 2, and Week 4. Fisher's exact test (2-sided p-values) will be used to test differences between netarsudil (0.01, 0.02% or 0.04%) versus placebo for each category at each visit. These analyses will be presented for both the ITT and PP populations with observed data only.

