4.2 Masking

Treatment assignments will be masked to the Investigator, the clinical study team (Sponsor, personnel involved in day to day study management, Monitors, Data Managers, and Statisticians), and the subjects for the duration of the study. Only in case of medical emergency or occurrence of AEs that warrant unmasking in the opinion of the Investigator, will the treatment assignment(s) be unmasked and made available to the Investigator and the Sponsor Medical Monitor or designee. Individual unmasking by the Investigator will normally result in withdrawal of the subject from the study and should only be performed for the specific subject requiring unmasking. In the absence of medical need, the randomization code will not be available to the above personnel until after the study is completed and the database is unlocked.

5. Sample Size and Power Considerations

Assuming a two-sided test with alpha = 0.05, a common standard deviation (SD) of 3.5 mmHg at each time point yielding a common SD of 3.0 for the diurnal mean, and a correlation among time points of 0.60, 49 intent-to-treat (ITT) subjects per arm yields at least 90% power to demonstrate superiority of netarsudil (0.01%, 0.02%, or 0.04%) to placebo in mean diurnal study eye IOP (average of 09:00, 11:00, and 16:00 hours) at the Week 4 visit assuming a difference of at least 2.0 mmHg in the mean diurnal IOP. Accounting for approximately a 5% discontinuation rate, 52 subjects per arm (208 total) will be enrolled.

6. Data Preparation

Study data will be recorded via electronic case report forms (eCRF). Each authorized study staff member will receive a unique access account in order to use the Electronic Data Capture (EDC) system. Access accounts will not be shared among study staff. Authorized users will make entries and/or changes to the eCRFs via a secure internet access. Each completed set of eCRFs will be reviewed by the Investigator

who will then electronically sign and date the eCRF confirming that data for the subjects are complete and accurate.

Final analyses outlined in this document will be carried out after the following have occurred:

- All data management requirements are met according to [REDACTED] standard operating procedures, including data entry, performance of edit and validation checks, documentation and resolution of data queries, and database lock with written authorization provided by appropriate [REDACTED] and Sponsor personnel.

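### As a continuous endpoint, percent change in IOP has no baseline-adjusted analysis; adding the existing ANCOVA beside the t-test is a small, cheap improvement

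*SAP*

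**What the plan says.** SAP Section 13.2 names four endpoints for "Two-sample t-test and 95% t-distribution confidence intervals on the difference" between each concentration and placebo: absolute change and percent change, each for the diurnal mean and at each time point. In Table 13-1 the two percent-change rows are marked for the t-test alone, on the ITT population with observed data.

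Protocol Section 9.6.2 agrees: "Mean percent change from baseline in mean diurnal IOP and mean percent change from diurnally adjusted baseline IOP at each time point" are to be compared by two-sample t-tests.

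Mean IOP is handled differently. The diurnal mean at Weeks 1, 2 and 4 and IOP at every time point get what footnote b of Table 13-1 describes as an "ANCOVA model including treatment as the main effect and baseline as the covariate". IOP at the time points also gets an MMRM with time-matched baseline. Protocol Section 9.6.2 gives the reason for adjusting only mean IOP: in a baseline-adjusted model, inference on IOP and on change from baseline is the same.

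Percent reduction is also analysed in categories, from 5% to 40%, by Fisher's exact test. That test is unadjusted too.

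The SAP cites protocol Amendment 2, and the protocol at hand is Amendment 1. SAP Section 18 lists only a change in the p-value inequality, so nothing suggests that the percent-change method differs between amendments.

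**The concern.** The protocol's reason covers absolute change. If Y is follow-up IOP, B is baseline and T is treatment, then Y = a + τT + βB implies Y − B = a + τT + (β − 1)B, with the same τ. Percent change divides by B, so the same model becomes 100(a + τT)/B + 100(β − 1), which is a different response and a different contrast. An adjusted analysis of mean IOP therefore does not stand in for one of percent change.

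Dividing by baseline removes the dependence on baseline only if follow-up IOP is proportional to it. With regression to the mean, eyes that start high tend to show larger percent falls whatever the treatment. The entry floors in Protocol Section 4.2 differ by diagnosis (15 mmHg for OAG, 22 mmHg for OHT), and randomisation is stratified by site only. Chance differences in baseline between arms are therefore not controlled by design. At stake are some precision and some protection against such a difference in a secondary endpoint. The superiority rule is not involved.

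**Working it through.** **The plan's own figure.** SAP Section 5 gives no precision for percent change, only the sample size for mean diurnal IOP. Its variability input is "a common standard deviation (SD) of 3.5 mmHg at each time point yielding a common SD of 3.0 for the diurnal mean". The other inputs are a 5% two-sided level, a within-visit correlation of 0.60 and a 2.0 mmHg effect. Its result is that "49 intent-to-treat (ITT) subjects per arm yields at least 90% power".

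- SD of a three-point mean: 3.5 × √((1 + 2 × 0.6)/3) = 2.997, which matches 3.0.
- n per arm by the normal approximation: 2 × (1.960 + 1.282)² × 3.0²/2.0² = 47.3, so 48. At 49 the t-based power is 90.4%.
- Enrolment: 49/0.95 = 51.6, so 52.

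The stated figures reproduce. The 0.60 is the correlation among time points. It is not the baseline-to-follow-up correlation, which the documents do not give.

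**Assumptions for percent change (not in the documents).** Baseline mean 20 and SD 3.0 mmHg, truncated at 15; follow-up SD 3.0; baseline-to-follow-up correlation ρ from 0.4 to 0.8; mean fall 1 to 5 mmHg. The calculation is for the diurnal mean. The time-point version has its own correlation, also not given.

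**Slope on baseline.** To first order, the slope of percent change on baseline is 100 × (ρ/20 − mean follow-up/20²). At ρ = 0.6 and a 3 mmHg fall this is 100 × (0.0300 − 17/400) = −1.25 points per mmHg. Simulation with the truncation gives −1.2. Over the grid it runs from −2.7 to +0.2.

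**Share of variance explained by baseline (R², simulated).**

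| ρ | fall 1 mmHg | fall 3 mmHg | fall 5 mmHg |
|---|---|---|---|
| 0.4 | 0.21 | 0.15 | 0.10 |
| 0.5 | 0.17 | 0.11 | 0.06 |
| 0.6 | 0.13 | 0.07 | 0.03 |
| 0.7 | 0.08 | 0.03 | 0.004 |
| 0.8 | 0.045 | 0.005 | 0.005 |

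**Effect on interval width.** The half-width shrinks by 1 − √(1 − R²).

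- Largest: 1 − √0.79 = 11%.
- Central (R² = 0.069 before rounding): 1 − √0.931 = 3.5%, worth 49 × 0.069 = 3.4 subjects per arm.
- Smallest: 1 − √0.996 = 0.2%.

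**Four-arm pooling.** At 49 per arm the t critical value falls from 1.985 (96 df) to 1.972 (191 df), and 1 − 1.972/1.985 is about 0.6%. This assumes equal variances across arms.

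**In percentage points, central case.** The simulated SD of percent change is about 12.6.

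- t-test half-width: 1.985 × 12.6 × √(2/49) = 5.05.
- With the covariate: 5.05 × √0.931 = about 4.88.
- With pooling as well: 4.88 × 1.972/1.985 = about 4.84.

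**Chance imbalance.** One standard error of the baseline difference is 3.0 × √(2/49) = 0.61 mmHg. It moves the unadjusted contrast by 0.61 × 1.2 = about 0.7 points, against a half-width near 5.

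**Sensitivity.** With baseline mean 18 to 24, baseline SD 2 to 3, ρ of 0.5 to 0.8 and a fall of 1 or 4 mmHg, the covariate gain runs from 0% to about 12%. At ρ = 0.3 it reaches about 18%.

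**The case against.** The strongest reply is that this is a preference. The t-test is valid under randomisation, prespecified, and the same in both documents. Percent change re-expresses IOP data that already receive adjusted analyses, and it plays no part in the superiority rule or the sample size. All of that stands, and it limits the point to an optional improvement.

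A second objection is that the proposed model is misspecified. The slope depends on the fall: at ρ = 0.6 it is 100 × (0.03 − 19/400) = −1.75 for a 1 mmHg fall and 100 × (0.03 − 15/400) = −0.75 for a 5 mmHg fall. If the drug works, slopes differ by arm. This is true but does little harm here. I simulated 6,000 trials with 49 per arm and mean falls of 1, 3, 4 and 5 mmHg, comparing the last arm with the first. The common-slope ANCOVA showed no material bias. At ρ = 0.6 its mean half-width was 4.86 against 5.06 for the t-test, with coverage of 94.8% and 95.1%. At ρ = 0.8 the two methods were equally precise. These are results for the scenarios tried, not a general guarantee.

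A third objection is cost in interpretation. The addition brings 3 × (3 + 9) = 36 more contrasts to a plan without multiplicity adjustment. The SAP also describes some analyses as already performed (Sections 13.3 and 20), so replacing the prespecified method now would itself be post hoc. This stands, and it is why the t-test should stay.

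A reader might go further and infer that the intervals are materially too wide, that baseline is ignored altogether, or that imbalance carries over in full. The documents support none of these. Baseline is the denominator, so part of its influence is already removed. The correlation that sets the gain is not stated, and the gain can be close to zero.

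**Conclusion.** The point holds as a minor one. Continuous percent change is the only continuous efficacy family without a baseline-adjusted analysis, and the protocol's reason for restricting adjustment does not extend to it. The gain is about 0 to 11% in interval width and about 3.5% in the central case. That rests entirely on assumed baseline values, correlation and fall. Pooling contributes about 0.6% and is not a reason to act by itself.

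This is a matter of efficiency and robustness to chance imbalance. It is not an error: the planned t-test remains valid, and the primary analysis and success criterion are unaffected.

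**What to change.** In SAP Section 13.2 and the two percent-change rows of Table 13-1, add the ANCOVA already used for mean IOP: treatment and the corresponding baseline, all four arms, ITT, observed data. Use the baseline diurnal mean for the diurnal endpoint and the time-matched baseline for each time point. Keep the prespecified t-test beside it, and report the ANCOVA next to it in Table 14.2.4.1 or in a companion table.

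Record the analysis as added in SAP Section 20. If it is added after unmasking, mark it as post hoc, as Section 21 does for other tables.

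The model is already programmed and baseline is already collected, so the work is a few lines of SAP text and one set of output columns. The remaining cost is one further set of secondary contrasts without multiplicity adjustment.

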Cornea verticillata, a whorl-like pattern of deposits typically localized to the basal corneal epithelium ([Mantjarvi 1998](#); [Hollander 2004](#)) have been reported in Aerie's completed Phase 3 studies ([AR-13324-CS301](#), [AR-13324-CS302](#), [AR-13324-CS303](#), and [AR-13324-CS304](#)). A variety of cationic, amphiphilic drugs are known to induce cornea verticillata, which arise due to the accumulation of phospholipids within corneal epithelial cells through a process called phospholipidosis (PLD). Amiodarone, an antiarrhythmic agent, is the most common cause of cornea verticillata, followed by chloroquine, hydroxychloroquine, indomethacin, and phenothiazines ([Raizman 2017](#)). It is unusual for these deposits to result in reduction of visual acuity or ocular symptoms, and the deposits typically resolve with discontinuation of the drug ([Mantjarvi 1998](#)). Corneal changes due to amiodarone have been studied over a long period of time and are well characterized; it is of

note that no routine monitoring, or specific treatment, or precautions are recommended for amiodarone-induced cornea verticillata ([Ingram 1982](#), [Siddoway 2003](#)).

The corneal verticillata associated with the use of netarsudil were first detected between 2-13 weeks, dose dependent, observed in 16.7% (76/454) of netarsudil QD subjects and 25.3% (64/253) of netarsudil BID subjects. Aerie carried out an observational cohort study ([AR-13324-OBS01](#)) to follow up the cases of cornea verticillata and demonstrated that cornea verticillata did not have any clinically meaningful impact on visual function and appeared to resolve after dosing was discontinued.

As part of the development plan in Japan, a Phase 1 ocular and systemic safety study comparing netarsudil ophthalmic solution 0.02% and 0.04% to placebo after a single dose and daily QD dosing over a 7-day period ([AR-13324-CS104](#)) in patients of Japanese ethnicity was recently completed in the United States. The study results demonstrated that the netarsudil 0.02% and 0.04 % formulations were safe and generally well tolerated by the healthy volunteer subjects of Japanese ethnicity within the 2nd generation who participated in this study.

The present study is a Phase 2 study to assess the efficacy and safety of netarsudil ophthalmic solution (0.01%, 0.02% and 0.04%) compared to placebo over a 28-day period in subjects with open-angle glaucoma (OAG) or ocular hypertension (OHT) in Japan.

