Randomized subjects will dose the assigned drug in both eyes QD in the evening (between 20:00 and 22:00 hours) beginning on Day 1 and up to and including the evening prior to the final visit at Visit 6 (Week 4). Procedures conducted at each of the Study Visits 4 to 6 will include safety and efficacy measurements, including IOP assessments. At Visits 4 to 6 (Weeks 1, 2, and 4, respectively), IOP will be assessed at 09:00, 11:00, and 16:00 hours. Following completion of the Visit 6 (Week 4) study visit procedures, subjects will exit the study. For subjects who discontinue early, every possible effort will be

made to assure there is a final visit that includes all examinations listed for Visit 6.0 (Week 4) and dilated ophthalmoscopy.

For subjects who show any evidence of cornea verticillata by slit lamp examination using the grading system for amiodarone keratopathy (Orlando 1984) during the 28-day treatment period, the assigned study drug will be discontinued, all exit visit procedures (Visit 6) will be completed and subject will be followed in an observational period starting as OBS Visit 1 (Day 1) in which subjects will undergo VFQ-25, BCVA testing, CS testing and cornea verticillata grading. All subjects with cornea verticillata will return for monthly surveillance visits (OBS Visit 2, 3 and 4) where they will undergo BCVA testing and cornea verticillata grading for 3 months. If cornea verticillata persists at the 3-month time point (OBS Visit 4), subjects will return every 2 months for BCVA testing and cornea verticillata grading until resolution or stabilization. Resolution is defined as grading of zero of the cornea verticillata grading and stabilization is defined as no worsening of the cornea verticillata grading for a minimum of one year from the commencement of dosing. Once resolution or stabilization is confirmed in both eyes, the subject will undergo VFQ-25, BCVA testing, CS testing and exit the study.

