3.2 Schedule of Visits and Assessments

The schedules of visits and assessments are provided below.

Table 3-1. Schedule of Visits and Assessments for the Treatment Period

Treatment Period

Day (D)/Week (W)	Screening	Qual. #1	Qual. #2 (Day 1)	W1 (Day 8±2)	W2 (Day 15±3)	Post Day 1 Treatment	W4 ¹ (Day 29±3)
Visit	1	2	3.0	3.1	3.2	4.0	4.1
Hour (XY = XY:00)	--	09	09	11	16	09	11
Informed Consent	X						
Inclusion/Exclusion	X	X	X	X			
Washout ²	X						
Demography	X						
Medical/Ophthalmic History	X	X	X				
Concomitant Medications	X	X	X	X	X	X	X
HR/BP	X	X	X	X	X	X	X
Urine Pregnancy Test ³	X						X
Clinical Labs (Chem/Hem/UA)	X ⁴						X
Symptoms/AEs ⁵	X	X	X	X	X	X	X
NEI VFQ-25 Questionnaire		X					
BCVA	X	X	X	X	X	X	X
Contrast Sensitivity		X					
TOP	X	X ⁶	X ⁶	X ⁶	X	X	X
Biomicroscopy	X	X	X	X	X	X	X
Gonioscopy ⁷ / Pachymetry ⁸	G/P						
Visual Field ⁹	X						
Ophthalmoscopy (dilated)	X						X
Eye-Drop Instillation Evaluation	X						
Study Medications Dispensed				X			
Study Medications Collected					X ¹⁰		X
Study Completed							X

Abbreviations: HR/BP = heart rate/blood pressure; Chem/Hem/UA = Chemistry/Hematology/Urinalysis; AE = adverse event; IOP = Intraocular pressure.
Early Discontinuation: Visit 6.0 procedures are to be completed plus a dilated ophthalmoscopy examination.
Visit Requirements: + IOP measurements will be 09:00 (+30 mins), 11:00 (+30 mins) and 16:00 (± 30 mins) hours with the exception of the Visit 1 (Screening).

1. If subjects develop cornea verticillata at visit 4 or visit 5, study procedures for visit 6 (Exit Visit) will be completed before entering into the observational period.
2. Subjects currently using ocular hypotensive medications must undergo a minimum washout period (see Section 5.7.1).
3. Urine pregnancy test for women of childbearing potential is required.
4. For subjects who are unable or unwilling to have blood drawn and urine collected for clinical labs at Visit 1 (Screening), the blood and urine sample may be drawn at Visit 2 (Qualification Visit #1) so long as the results of the clinical labs are available for that subject prior to Visit 3 (Qualification Visit #2).

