7.1 Intent-to-Treat Population

The ITT population will include all randomized subjects who have received at least one dose of study drug. This population will be the primary population for efficacy analyses and will be used to summarize all efficacy variables and will summarize subjects as randomized.

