8.5 Assessment Time Windows

In general, it is intended that all safety and efficacy data (with some exceptions) will be summarized at each time point collected regardless of assessment time windows. Because subjects may have an early termination visit at any time or may have unscheduled visits, the following conventions will be implemented.

For all safety and efficacy data, unscheduled visits are not included in the analyses unless they are considered as baseline.

The assessment visit date or start date (e.g., AEs) will be used to calculate study day, defined as the number of days from the day of first dose (Visit 3). The day of first dose (Visit 3) is considered study day 1, so study day will be computed as: (Date of Assessment Data – Date of Visit 3) + 1.

In all by-visit safety assessments, end of study visits and early termination visits will be combined in order to present all data available for each subject; early termination visits will not be windowed into the nearest fitting study visit. Each subject will have one end of study visit.

For efficacy outcomes, early termination data will not be combined with end of study visit information as the timing of the outcome measure is integral to the analysis. Instead, the efficacy outcome will be windowed into the nearest study visit, where Visit 4 has a \pm 2 day window, and Visit 5 and Visit 6 have a \pm 3 day window.

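### Responder percentages labelled ITT use observed data only, with no missing-data analysis; part of the Week 4 loss is treatment-related, but its effect on the comparison is not established

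*SAP*

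**What the plan says.** SAP 13.2 counts study eyes at or below each of a series of mean diurnal IOP levels, and study eyes reaching each of a series of absolute and percent reductions, at Weeks 1, 2 and 4. Fisher's "exact test (two-sided p-values) will be used to test differences between netarsudil" doses and placebo in every category. On missing data it says: "These analyses will be presented for both the ITT and PP populations with observed data only". The matching row of Table 13-1 and the title of Table 14.2.5.1 agree, and Protocol 9.6.2 has the same rule. Neither document states the denominator in words.

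Four other provisions bear on who is missing:

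- SAP 7.1: "The ITT population will include all randomized subjects who have received at least one dose of study drug".
- SAP 8.2, as the general rule, puts multiple imputation first and treats observed data and LOCF as secondary.
- SAP 3.1, for any verticillata seen in the 28 days: "the assigned study drug will be discontinued, all exit visit procedures (Visit 6) will be completed".
- SAP 8.5: "For efficacy outcomes, early termination data will not be combined with end of study visit information". It continues: "Instead, the efficacy outcome will be windowed into the nearest study visit", with ±2 days for Visit 4 and ±3 days for Visits 5 and 6.

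**The concern.** A percentage labelled ITT but computed on observed data describes only the subjects who have a value at that visit. Someone stopped before Week 4 is neither a responder nor a non-responder there. For most causes of loss this might be minor, but here one cause is written into the design and tied to the drug. Protocol 1.1 describes verticillata on netarsudil as "first detected between 2-13 weeks, dose dependent, observed in 16.7% (76/454) of netarsudil QD subjects". If stopped subjects would have done worse, or if stopping is itself regarded as failure, the active rates look better than the ITT rates, most so at the dose with the most early stops. The study title includes choosing an optimum concentration, so comparison between doses matters even for a secondary endpoint. The plan contains no second responder analysis that would show whether the handling changes the answer.

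**Working it through.** **1. The plan's own figures.** The documents give none for the responder analysis: no expected rate, no loss by arm. The sample size supplies the arm size and overall loss, and it reproduces:

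- SD of a three-reading mean = 3.5 × √((1 + 2 × 0.60)/3) = 2.997, stated as 3.0.
- 49 per arm and a 2.0 mmHg difference give 90.4% power by t-test.
- 49/0.95 = 51.6, so 52 per arm. A 5% loss is 0.05 × 52 = 2.6 subjects per arm.

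**2. Who lacks a Week 4 diurnal mean.**

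- *Verticillata found at Visit 4 or 5.* Exit procedures are done then and the IOP is windowed to that visit, so Week 4 is empty. First detection is put at 2–13 weeks. Visit 4 (Day 8 ± 2) falls before that range and Visit 5 (Day 15 ± 3) at its lower end.
- *Verticillata first found at Visit 6.* No Week 4 value is lost.
- *Other early discontinuation.* SAP 3.2 says "Visit 6.0 procedures are to be completed plus a dilated ophthalmoscopy examination". Visit 6.0 carries only the 09:00 reading, whereas Protocol 9.6.2 builds the diurnal mean from three.
- *Weeks 1 and 2.* Data up to the stopping visit still count, so the loss is smaller.

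**3. Effect on one arm.** Let d be the fraction missing, p the observed rate, and q the rate the missing subjects would have had. The all-ITT rate is p(1 − d) + qd, so the gap is d(p − q). With assumed p = 0.50 and d = 0.05:

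| Assumption about the missing | q | Gap, points |
|---|---|---|
| All failures | 0 | 0.05 × 0.50 = 2.5 |
| Half as likely to respond | 0.25 | 0.05 × 0.25 = 1.25 |
| Same as those observed | 0.50 | 0 |
| A quarter more likely | 0.625 | −0.6 |

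In whole subjects, with missing as failure: 3 of 52 lost (5.8%) turns an observed 40% into 0.40 × 49/52 = 37.7% and 60% into 56.5%. Five of 52 lost (9.6%) gives 36.2% and 54.2%.

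**4. Effect on the comparison.** The error in active minus placebo is dA(pA − qA) − dP(pP − qP), where A is active and P placebo. Its sign depends on losses and response rates that the documents do not give. Lack of efficacy is a listed reason to discontinue (Protocol 6.20.2). Such exits have low q, and on placebo they raise the second term.

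**5. Effect on a p-value (assumed counts).**

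- 24 active responders against 15/52 on placebo: on 24/49 observed, Fisher p = 0.043; on 24/52 with the three missing as failures, p = 0.105. Had two of the three responded, 26/52 gives p = 0.044.
- Suppose both arms have a 40% rate with missing as failure, and placebo is complete. Exact enumeration puts two-sided rejection on observed data at 3.5% with none lost, 5.2% with 3 lost and 6.3% with 5 lost.

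There are 9 level, 5 absolute-reduction and 8 percent-reduction thresholds. That makes 22 × 3 doses = 66 such tests at Week 4.

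**The case against.** A reader might infer that the active response rates are inflated. The documents do not support that. Verticillata is a corneal tolerability event, and nothing in either document ties it to a poor IOP response; if q = p the gap is zero. No loss by arm, placebo verticillata rate or 28-day rate is given. The dose dependence is illustrated by once- against twice-daily dosing (76/454 and 64/253), not by concentration.

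A reader might also carry the 16.7% across as Week 4 loss, which at 50% would be 0.167 × 50 = about 8.4 points. That does not fit: the figure covers detection out to 13 weeks, only findings before Visit 6 cost Week 4 data, and the plan expects about 5% discontinuation overall. Nor is the denominator simply completers; it is whoever has a value at that visit.

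The endpoint is secondary, untested for success and unadjusted in Phase 2. The rule is disclosed and identical in protocol and SAP. The underlying continuous variables, mean diurnal IOP and its change from baseline, are analysed with MCMC, LOCF and observed data. Counting missing as failure changes the question rather than correcting an error. All of this stands, and it limits the size and certainty of the point.

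It could be added that the disposition table will reveal any imbalance. That is only partly so. Protocol 6.20.1 treats a subject with verticillata who finishes the observational visits as completed, and SAP 9 tabulates discontinuation from the study. Such a subject may therefore appear there as a completer while having no Week 4 value.

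**Conclusion.** The point holds as a gap in the plan. Tested responder percentages carry an ITT label, omit ITT subjects without a value, and have no missing-data analysis, contrary to the SAP's own general rule. Part of the omission comes from a mandatory stop for an event linked to the drug, so it could favour active doses. Bias in that direction is not shown.

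At the planned 5% loss and an assumed 50% rate, the shift in one arm lies between zero (q = p) and 2.5 points (q = 0), and is slightly negative if the missing would have responded better. The response rates and counts lost are assumptions. A shift of this size can still move a nominal Fisher result across 0.05. The primary analysis and the success criterion are unaffected, so this is an improvement worth making rather than a threat to the trial's conclusion.

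**What to change.** In SAP 13.2, Table 13-1 and Table 14.2.5.1:

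- State the denominator at each visit.
- Add an all-ITT responder analysis in one or both of two forms: responders derived from the MCMC data sets already planned in SAP 13.1, and missing counted as non-response. The MCMC model takes missing subjects to resemble observed ones given treatment and baseline, so the two forms roughly span q near p to q = 0.
- For the imputed form, pool the difference in proportions and its standard error through the existing MIANALYZE step, since Fisher p-values do not combine by the usual rules.
- Label the non-response form as a composite of IOP response and tolerability.
- Keep the observed-data table as supportive, with missing counts by arm and reason, showing verticillata separately.

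The cost is one extra derivation and one added table, with no new data. Active-arm rates may look slightly less favourable.
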